2.0 OBJECTIVES

2.1 Primary Objective

- Evaluate whether CIP can reduce progression of critical illness among patients hospitalized for COVID-19

2.2 Secondary Objectives

- Evaluate safety of CIP
- Evaluate cellular and humoral responses before CIP treatment and at CIP treatment.
- Evaluate the effect of CIP as compared to non-transfused immunologic control patients.

2.3 Study Design

This is a single arm phase II trial to assess preliminary efficacy and confirm safety of infusions of anti-SARS-CoV-2 convalescent plasma in hospitalized patients with acute respiratory symptoms **with or without** confirmed interstitial COVID-19 pneumonia by CXR or chest CT. A total of 29 eligible subjects will be enrolled to receive high titer anti-SARS-CoV-2 plasma. Participants will be compared to a historical control group via retrospective chart review.

In addition, the following Immunologic Controls will be used to meet secondary objectives described above:

1. PBMCs with 5-10 million cryopreserved cells per specimen will be obtained from the prospective COVID 19 Biorepository (2 timepoints per patient t (60 specimens total) and assessed for cellular and humoral immune responses.
2. Serum or plasma 500 UI each from up to 50 patients in the Covid-19 Biorepository will be collected (2 timepoints from each patient) (100 total specimens) will be evaluated for antibody and cytokine responses.

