Drug: Pathogen reduced SARS-CoV-2 convalescent plasma (1-2 units; 2 units are preferable but a single unit is allowable in the setting of safety/time/resource/etc concerns; ~200 mL each for a total of upto ~400 mls) given preferably in one day, but allowable to be given over 2 days if clinical circumstances delay infusions in 1 day), with titer to be determined after the unit has been infused.

Directed Donor Plasma Units: Healthy donors who have recovered from COVID-19 infection 21 days after symptom resolution will undergo a donor eligibility questionnaire. If eligible, blood will be drawn for ABO typing, HLA antibodies, and infectious disease panel screening. One additional red top tube will draw and sent to the [name] laboratory at UVA to test for levels of IgG anti-COVID-19 spike protein. No OP or NP PCR testing will be performed at day 21 given that donation will occur at day 28 or after. If the donor is eligible and matched, they will be called back to donate plasma at the ARC on day 28 after symptom resolution or later. The ARC or other local facility will collect blood for ABO, HLA, and infectious disease panel screening obtained via Emergency Use Authorization.

Immune Evaluations: Immune evaluations will be performed to determine if infusions of immune plasma enhance the development of anti-COVID-19 immune responses: peripheral blood mononuclear cells (PBMC) will be cryopreserved for measurements of specific anti-COVID-19 IFN-γ ELISpots, single cell high-dimensional immunophenotyping by mass cytometry and RNA-Seq; specific serum IgG, IgM and IgA antibodies COVID-19 and levels of Th₁/Th₂ serum cytokines at the designated time points at 0, 14, and 28 days after CIP infusion.

i. List of Abbreviations

ADR Adverse Drug Reaction

² Measured by an anti-SARS-CoV-2 ELISA and serum antibody titer to SARS-CoV-2.

ADE	Antibody-mediated enhancement of infection
BP	Blood pressure
CIP	Convalescent Immune Plasma
CTCAE	Common Terminology Criteria for Adverse Events
DBP	Diastolic Blood Pressure
DLT	Dose limiting Toxicity
DSMB	Data and Safety Monitoring Board
ECG/EKG	Electrocardiogram
EUA	Emergency Use Authorization
FDA	Food and Drug Administration
GCP	Good Clinical Practice
HBV	Hepatitis B virus
HCV	Hepatitis C virus
HIV	Human immunodeficiency virus
HTLV	Human T-cell lymphotropic virus
IB	Investigator’s Brochure
ICF	Informed Consent (Informed Consent Form)
ICH	International Conference on Harmonization
ICU	Intensive Care Unit
IEs	Immune Evaluations

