3.0 BACKGROUND AND SIGNIFICANCE

3.1 Background and Scientific Rationale

There are no proven treatments for coronavirus disease (COVID-19) and associated pneumonia caused by Severe Acute Respiratory Syndrome Coronavirus 2 (SARS-CoV-2). Recent experience in China suggests that convalescent immune plasma (CIP) may be an effective treatment for COVID-19. In the pandemic situation where there are no vaccines for COVID-19, specific antibodies in convalescent plasma induced by infection may provide passive protective immunity. Passive antibody therapy was the first immunotherapy dating back to the 1890s for the treatment of infectious diseases before the development of antibiotics 1940s^{1, 2}. Experience from prior outbreaks with other coronaviruses, such as SARS-CoV-1 shows that such convalescent plasma contains neutralizing antibodies to the relevant virus³. In SARS-CoV-2, passive antibody therapy from CIP probably provided protection by viral neutralization. CIP was also used in the 2013 Ebola epidemic. A small non-randomized study in Sierra Leone revealed a significant increase in survival for who received CIP⁴. CIP administration is the only approach that provides immediate immunity to patients who have been exposed or who have active disease.

This approach is immediately available from individuals who have recovered, are viral free, and can donate immune plasma (IP) containing high titer neutralizing antibodies. Passive antibody therapy can be given to a patient recently exposed or a patient who is developing an infection with COVID-19 by obtaining plasma units from immune individuals by standard plasmapheresis using FDA-approved blood banking procedures, cross matching the unit(s) to the recipients and infusing the unit(s) using standard

transfusion procedures for blood products. Based on the safety and long-term experience with plasma infusions, plasma exchanges, and other procedures involving plasma or plasma product, this protocol was designed as a phase II single arm trial that involves the administration of antibodies to a given agent to a susceptible individual for the purpose of preventing or treating an infectious disease due to that agent.

The only antibody formulation that is available for emergent use is that found in convalescent plasma. As more individuals contract COVID-19 and recover, the number of potential donors will increase.

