The principle of passive antibody therapy is that it is more effective when used for prophylaxis than for treatment of disease. When used for therapy, antibody is most effective when administered shortly after the onset of symptoms. The reason for temporal variation in efficacy is not well understood but could reflect that passive antibody works by neutralizing the initial inoculum, which is likely to be much smaller than that of established disease. Alternatively, antibodies may dampen the early inflammatory response leaving the infected individual asymptomatic⁵. For example, antibody therapy for pneumococcal pneumonia was most effective when given shortly after the onset of symptoms and was of no benefit if antibody therapy was delayed beyond the third day of disease⁶. For passive antibody therapy to be effective, a sufficient amount of antibody must be infused. The antibody will circulate in the blood, reach tissues, and provide protection against infection. Depending on the type of antibody, amount, and composition, the half-life can vary from weeks to months. It is under these circumstances, *we plan to treat patients who are sick enough to be hospitalized before the onset of overwhelming disease involving a systemic inflammatory response, sepsis, and/or ARDS.*

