3.2 Experience with the use of convalescent immune plasma against coronavirus diseases

In the 21st century, there were two coronavirus epidemics associated with high mortality. The SARS outbreak in 2003 and MERS outbreak in 2012 had high mortalities and absence of effective therapies which led to the use of convalescent immune plasma. The largest study with SARS using convalescent immune plasma involved the treatment of 80 patients in Hong Kong⁷. **Patients treated before day 14 after onset of symptoms had an improved prognosis as measured by discharge from hospital before day 22.** Furthermore, those who were RT-PCR positive and seronegative for coronavirus at the time of therapy had improved prognosis. Three seriously ill patients recovered from SARS in Taiwan were treated with 500 ml of convalescent plasma which led to a reduction in plasma virus titer⁸. Three patients with MERS in South Korea were treated with convalescent plasma, but only two of the recipients had neutralizing antibody in their plasma⁹. The results suggests that providing passive antibodies may suppress the development of high titers of neutralizing antibodies to the pathogen¹⁰. The analysis of 99 samples of convalescent sera from patients with MERS showed that 87 had neutralizing antibody with a geometric mean titer of 1:61. These data suggest that antibody declines with time and/or that few patients make high titer responses. There are reports that convalescent plasma was used for therapy of patients with COVID-19 in China during the current outbreak. Although few details are available from the Chinese experience and published studies involved small numbers of patients, the available information suggests that convalescent plasma administration reduces viral load and was safe. Because of these early suggestions of benefit, it is ethically complex to conduct a placebo-controlled trial, therefore we propose to use a comparator group of patients who have been treated at UVA Medical Center prior to the start of this trial.

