6.0 PREPARATION OF CONVALESCENT IMMUNE PLASMA

The plasma product will be collected from **directed**-donors or anonymous donors from the American Red Cross, New York Blood Center, or other local blood donation facility 28 days after symptom resolution. Antibody titers may be assessed by prescreening 21 days after symptom resolution with an anti-SARS-COV-2 titer of preferably >1:64 and/or by measuring titers from the infused plasma. We will use an FDA-approved test to measure antibodies, such as the Ortho Clinical Diagnostic or equivalent test for total IgG, IgM, and IgA directed at COVID-19 spike protein. Donors may be recruited from COIV-19 Screening Clinics, Employee Health Clinics within the health system and by social media advertising. Per current FDA recommendations and ARC practices, it is assumed that by day 28 after symptom resolution, that there will be no viable viral COVID-19 in the circulation. Otherwise the donor will fulfill all of the standard donor criteria for plasma donation.

Donors and samples will have been screened for transfusion-transmitted infections (e.g. HIV, HBV, HCV, WNV, HTLV-I/II, T.cruzi, ZIKV) both through the use of the uniform donor questionnaire and FDA mandated blood donor screening tests. Plasma will have been collected by the ARC or local donation site using standard apheresis technology and in accordance with standard FDA and blood bank protocols. The CIP will be in standard plasma unit bags with storage, handling, and release per blood bank guidelines. The patient will receive 1-2 units of anti-SARS-CoV-2 convalescent plasma.

Table Treatment Schedule	I: Screen n	Baseline	Transfusion	Follow-up							
				1	4±1	7±2	14±3	21±3	28±3	60±7	1 year
Day	-1 to	0	0	1	4±1	7±2	14±3	21±3	28±3	60±7	1 year

	0				day	day	days	days	days	days	±1 month ⁵
Eligibility											
Informed consent	x										x
Demographic and Medical history	x										x
COVID-19 symptom screen	x										
SARS-CoV-2 RT-PCR for eligibility	x										
Pregnancy test	x										
ABO	x										
Study Drug Administration											
Drug infusion			X								
Study Procedures											
Vital signs ⁴	x	x	Xxxx ³	x	x	x	x	x	x	X	
Physical examination ⁴	x		x	x		x		x		X	
Symptom screen ⁴	x	x	x	x	x	x	x	x	x	X	x
Concomitant medications ⁴	x	x	x	x	x	x	x	x	x	X	
Assessment with 8-point ordinal scale ⁴		x		x	x	x	x	x	x	X	
Adverse event monitoring ⁴		x	x	x	x	x	x	x	X	X	
Health Questionnaire											x
Laboratory testing											
CBC and CMP ⁴		x		x		x	x	x	X	X	X

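### The protocol describes the study plasma as high titer, but no antibody level is binding and no planned analysis uses the titer of the infused units

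*Combined protocol and SAP*

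**What the plan says.** **Description of the product.** Section 2.3: "A total of 29 eligible subjects will be enrolled to receive high titer anti-SARS-CoV-2 plasma". Section 5.1 repeats the description for the 1-2 units given, and Section 12.0 sets out to assess the safety of high-titer plasma. None of these sections gives a number.

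**What governs the product.**
- Section 6.0: "Antibody titers may be assessed by prescreening 21 days after symptom resolution with an anti-SARS-COV-2 titer of preferably >1:64 and/or by measuring titers" from the plasma that was infused. It also admits units from anonymous blood-centre donors.
- Sections 4.4 and 4.5: the donor inclusion and exclusion criteria contain no antibody item.
- Section 1.0, Directed Donor Plasma Units: a tube is drawn for anti-spike IgG. The call-back sentence then reads "If the donor is eligible and matched, they will be called back to donate plasma at the ARC", and the antibody result is not named as a condition.
- Section 1.0, Drug: the unit's titer is determined after it has been infused.

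**Rationale.** Section 3.1 says that "passive antibody therapy from CIP probably provided protection by viral neutralization" and that "For passive antibody therapy to be effective, a sufficient amount of antibody must be infused". Section 3.2 reports that "99 samples of convalescent sera from patients with MERS showed that 87 had neutralizing antibody with a geometric mean titer of 1:61", and adds: "These data suggest that antibody declines with time and/or that few patients make high titer responses".

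**Power and analysis.** Sections 7.1 and 9.1 test an ICU rate of 50% against 25% and reject 50% if 8 or fewer of 29 evaluable patients are admitted. The titer and immune analyses in Sections 9.1 and 9.4 concern the recipients' own samples. None uses the titer of the infused units.

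**The concern.** A patient given plasma with no detectable antibody would be treated fully within protocol. Under Section 10.9, a subject who discontinues after an infusion is not replaced. The design therefore does not guarantee a product property that it states in three places.

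This bears on the primary rule through dilution. If neutralization is the mechanism and a sufficient amount is needed, each recipient of ineffective plasma has an expected ICU rate nearer 50% than 25%, and the chance of seeing 8 or fewer transfers falls. If 9 or more patients are then transferred, the planned analyses do not relate that outcome to what was infused. The report would also describe as high titer a product that was never held to that standard.

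**Working it through.** **Inputs.** From Section 9.1: n = 29, null ICU rate 0.50, target rate 0.25, two-sided alpha 0.05, reject if X ≤ 8. From Section 3.2: 99 MERS convalescent sera, 87 with neutralizing antibody, so 99 − 87 = 12 without (12/99 = 12.1%). From Section 1.0: one or two units, two preferred.

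**Step 1. The plan's own figure.** The one-sample normal approximation gives

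n = [1.96·√(0.5·0.5) + 0.8416·√(0.25·0.75)]² / 0.25² = 28.9,

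rounded up to 29, with approximate power 80.1%. The stated 80% is reproduced. The printed rule evaluated exactly gives:
- P(X ≤ 8 | 29, 0.50) = 0.0121 one-sided, or 0.024 doubled
- P(X ≤ 8 | 29, 0.25) = 0.713

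The 71% is the reference below. Its gap from 80% comes from the cut-off of 8 and has nothing to do with titer.

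**Step 2. Dilution.** Let f be the share of recipients whose plasma has no effect. Assume an ICU rate of 0.25 with antibody-containing plasma and 0.50 otherwise. Then

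p = 0.25(1 − f) + 0.50f = 0.25 + 0.25f, and power = P(X ≤ 8 | 29, p).

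**Step 3. Results.**

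| Scenario | f | p | Exact power |
|---|---|---|---|
| All plasma has antibody | 0 | 0.250 | 71.3% |
| Two units from independent donors, both negative: (12/99)² | 0.015 | 0.254 | 69.6% |
| Lower 95% limit of 12/99 | 0.064 | 0.266 | 64.0% |
| One unit, or two from one donor: 12/99 | 0.121 | 0.280 | 57.3% |
| Upper 95% limit of 12/99 | 0.202 | 0.301 | 47.6% |

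The limits are Clopper-Pearson. The two-donor row assumes that one positive unit is enough for full effect.

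**Step 4. The other reading of 25%.** Section 9.1 does not tie the 25% to antibody-positive plasma. If 25% is the average rate for plasma as supplied, f is already inside it and power stays at 71.3%.

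**Step 5. Type I error.** If plasma has no effect at any titer, p = 0.50 for every f, so the one-sided error stays at 0.0121.

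**Step 6. What a titer subset could show.** At f = 12/99, 29 × 0.121 = 3.5 patients would be set aside, leaving about 25. For illustration, 9 of 29 has an exact 95% interval of 15% to 51%, and 7 of 25 has 12% to 49%. These overlap almost entirely.

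**The case against.** The case for leaving the plan alone has real weight.

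- **Supply.** A preferred rather than required titer is defensible when plasma is scarce and patients must be enrolled within 72 hours of admission. This stands against making 1:64 binding. It does not justify calling the product high titer, nor calling back a donor whose tube shows no antibody.
- **The 12/99 is not about this product.** It is a background figure for MERS sera. Section 3.2 offers waning over time as an explanation alongside few high responders, and Section 3.1 says that recovered donors can supply high-titer neutralizing plasma. A reader might infer that about 12% of study units will lack antibody. The documents do not support that, and they never set the figure as an expectation for SARS-CoV-2 plasma.
- **The loss may be negligible.** It is zero if 25% is the average effect of plasma as supplied, and under 2 points with two independent donors. This stands, and is why the power figures are illustrative.
- **Titers are already planned.** The Summary foresees determining unit titers, and Section 9.1 relates recipients' immune responses to ICU admission. Most of the measurement is therefore in place. What is missing is its use.

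A reader might also take the three-patient MERS report in Section 3.2, "but only two of the recipients had neutralizing antibody in their plasma", to mean that one donor unit in three fails. Read literally, the sentence is about the recipients' plasma, and the sentence after it concerns suppression of antibody development. It gives no donor failure rate.

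**Conclusion.** The point holds as a mismatch between the stated product and the operative rules, together with a gap in the analysis. No antibody level is binding, and no planned analysis uses infused-unit titer.

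The effect on power cannot be fixed from the documents. If the 25% rate applies only to antibody-containing plasma and other plasma has no effect, exact power is 71% with none ineffective, 70% at 1.5%, 57% at 12%, and 64% to 48% over the 95% interval of the MERS figure. If 25% is an average over plasma as supplied, nothing is lost.

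Two stronger readings are tempting. One is that 57% is a floor. It is one scenario, and the interval alone reaches 48%. The other is that a positive trial would be suspect. It would not: type I error is unchanged, and a rejection would stand as a result about plasma as given.

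The change should be made because its main parts are cheap, not because a particular loss has been shown.

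**What to change.** 1. **Donor call-back (Sections 1.0, 4.4 and 6.0).** Call back a directed donor only if antibody is detected on the anti-spike tube already drawn. Keep a titer above 1:64 as a preference, and record every untested blood-centre unit that is used. Cost: some directed donors are lost, about 12% on the MERS figure. The planned test measures binding antibody, which only partly tracks neutralization, so a return to 71% is not assured. Making 1:64 binding could lose about half of donors: with a geometric mean of 1:61, and log titers of the 87 positives assumed symmetric, (12 + 43.5)/99 = 56% lie at or below 1:61. It should remain a preference.
2. **Wording (Sections 2.3, 5.1 and 12.0).** Replace the high-titer description with: convalescent plasma, titer >1:64 preferred but not required. This is a text change only.
3. **Measurement and analysis (Sections 9.1 and 9.4).** Report the titers of all infused units on one named assay. Pre-specify one exploratory analysis of ICU transfer by infused-unit titer, with exact intervals and the assay run blind to outcome. State that it aids interpretation, does not replace the 8-of-29 rule, and cannot by itself explain a non-rejection. Cost: one assay must be fixed across blood centres.

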4.5 Exclusion Criteria for Plasma Donor

- Female subjects with positive pregnancy test, breastfeeding, or planning to become pregnant/breastfeed during the study period.

- Medical conditions for which plasma donation is not considered safe (presence of a blood borne pathogen, presence of HLA antibodies, etc)
- Other disqualifying condition as set forth by the American Red Cross blood/plasma donation policies.

Inclusion Criteria for Immunologic Controls

1. PBMCs with 5-10 million cryopreserved cells per specimen with 2 timepoints per patient
2. Serum or plasma 500 UI each (2 timepoints from each patient)

Exclusion Criteria for Immunologic Controls

Specimens not available through the COVID Repository protocol.

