9. Blood for Immune evaluations of cellular and humoral immunity (4 green tops, 30-40 milliliters).

Day 1-7 (or for duration of hospitalization)

1. Vital signs daily (including supplemental oxygen requirements)
2. COVID-19 symptom screen (fevers, cough, shortness of breath)
3. Assessment of clinical status (8-point ordinal scale)
4. New medical conditions, AE evaluation
5. Physical examination
6. CBC with differential, comprehensive metabolic panel, CRP daily

Days 0, 4 (\pm 1 day), 7 (\pm 2 day), 14 (\pm 3 days), 21 (\pm 3 days), and 28 (\pm 3 days):

1. SARS-CoV-2 PCR from oropharyngeal or nasopharyngeal swabs: Day 0, 4, 7, 14, 21 and at any time when there is clinical suspicion for COVID-19.
2. Serum or plasma antibody titer to SARS-CoV-2: Day 0, 7, 14, and 28
3. Blood for immune evaluations of cellular and humoral immunity before CIP infusion (day 0) and 7, 14, and 28 days after CIP infusion (4 green tops, 30-40 milliliters). Immune testing may be done at any time if the PI determines there is a need to evaluate acute immune responses (cytokines/chemokines levels).

Key issues to consider follow up by phone, alive, at home, in hospital (ICU or not), on supplemental O₂ or not, back to work, fully and partially

- COVID-19 symptom screen (fevers, cough, shortness of breath)
- Assessment of clinical status (8-point ordinal scale)
- New medical conditions, AE evaluation

Day 60 (\pm 7 days):

1. COVID-19 symptom screen (fevers, cough, shortness of breath)

2. Assessment of clinical status (8-point ordinal scale)
3. New medical conditions, AE evaluation

One year (\pm 1 month) - *optional*

- 1. Serum or plasma antibody titer to SARS-CoV-2**
- 2. Blood for immune evaluations of cellular and humoral immunity**
- 3. CBC with differential, Comprehensive metabolic panel, PT/INR, PTT, Quantitative immunoglobulins**
- 4. Interval medical history**
- 5. Subject questionnaires regarding health status**

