10.8 Immune Evaluations

Immune evaluations (IEs) will be conducted as delineated in Table 1. Baseline serum and cells will be aliquoted from the pheresis. Blood draws (4 green top tubes containing approximately 50 mL of anti-coagulated blood and 1 red top tube containing 8 mL of serum) will be collected at designated time points at 0, 7, 14, and 28 days after CIP infusion. All patients receiving any dose of study treatment should be assessed for immune markers. Evaluations will include:

- Serum cytokine/chemokine levels
- Phenotyping of T cells and T cell subpopulations, TCR repertoire analysis, monocyte, B cells, and NK cell by flow cytometry.
- Cytotoxic activity and IFN γ production in PBMC populations. An immune response will be defined as a 30 IFN γ Elispots per million cells plated above the background of unstimulated spontaneous IFN γ Elispots per million cells plated.
- Additional assays may be performed on available samples to evaluate Th₁/Th₂ responses in single cell RNA sequencing on selected samples.

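### Recipient cytokines are assayed in serum but control specimens may be serum or plasma, and the planned comparison does not account for specimen type

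*Combined protocol and SAP*

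**What the plan says.** **Recipients.** Section 10.8 lists "Serum cytokine/chemokine levels" among the immune evaluations, and the Summary refers to "levels of Th₁/Th₂ serum cytokines". Section 10.8 also provides the tube: "1 red top tube containing 8 mL of serum) will be collected at designated time points at 0, 7, 14, and 28 days". Section 8.3 has the same red-top tube beside the green-top anticoagulated ones.

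**Controls.** Sections 1.0 and 2.3 take biorepository specimens of either type: "Serum or plasma 500 UI each from up to 50 patients in the Covid-19 Biorepository will be collected". There are two timepoints per patient, 100 specimens in all, for antibody and cytokine responses. The inclusion criteria for immunologic controls, printed after section 4.5, repeat the choice: "Serum or plasma 500 UI each (2 timepoints from each patient". The only exclusion there is that a specimen is not available from the repository.

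**Comparison.** The third secondary objective (section 2.2) is the effect of convalescent plasma relative to these non-transfused controls. Section 9.1 says the recipient effects will be compared with the control biospecimens. It names age and co-morbidities as example covariates, waives multiplicity adjustment as exploratory, and sets p < 0.05 as significant.

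**Tube lists.** The visit schedule in section 5.2.7 names only "4 green tops, 30-40 milliliters" for recipients' immune blood. Sections 8.3 and 10.8 add the red-top tube.

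**The concern.** The rule for accepting control specimens can tie specimen type to treatment group. All recipient cytokine values are meant to come from serum; any share of the control values, from none to all, may come from plasma. If the two types give different readings for an analyte, a recipient-control difference in levels contains two parts that the data cannot fully separate: the effect of convalescent plasma and the effect of the tube. If every control is plasma, they cannot be separated at all.

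This is a bias, so more controls would not dilute it. Calling the analysis exploratory explains the missing multiplicity correction but does not remove a systematic shift, and section 9.1 still applies a significance threshold. At stake is the cytokine part of the third secondary objective.

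**Working it through.** **1. The plan's own figure.** Up to 50 control patients x 2 timepoints = 100 specimens, which agrees with section 2.3. The plan states no power for the cytokine comparison.

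**2. Which comparisons have the mismatch.**

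| Measure | Recipients | Controls | Type tied to group? |
|---|---|---|---|
| Cytokines | Serum (Summary, 10.8) | Serum or plasma (1.0, 2.3, criteria after 4.5) | Yes, if any control is plasma |
| Antibody titer | Serum or plasma (1.0, 5.2.7, 7.3.2) | Serum or plasma | Not by the text |
| Recipients' pre/post tests (9.1) | Recipients only | None | No |
| ICU transfer, 28-day mortality | Clinical | Clinical chart review | No |

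**3. Bias in a comparison of levels.** Let r be the serum-to-plasma ratio for an analyte, s the between-patient SD on the natural-log scale, and f the share of controls in plasma. With no true treatment effect, the expected difference between groups is f x ln(r), or f x ln(r)/s in SD units. It is zero if f = 0 or r = 1.

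**4. False-positive rate.** From the documents: 29 recipients, up to 50 controls, two-sided 0.05. Assumed, because the documents are silent: r from 1.25 to 2, s from 0.7 to 1.0, f of one half or one, and a two-sample t-test on log values. Rates come from simulation with at least 20,000 replicates per cell. Each range runs from s = 1.0 to s = 0.7.

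| r | ln(r) | ln(r)/s | Half of controls plasma | All controls plasma |
|---|---|---|---|---|
| 1 | 0 | 0 | 5% | 5% |
| 1.25 | 0.223 | 0.223-0.319 | about 7-10% | about 16-27% |
| 1.5 | 0.405 | 0.405-0.579 | about 13-22% | about 40-69% |
| 2 | 0.693 | 0.693-0.990 | about 29-50% | about 83-99% |

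Hand check of the two extremes with all controls in plasma. The standard error in SD units is sqrt(1/29 + 1/50) = 0.233.
- r = 1.25, s = 1.0: 0.223/0.233 = 0.96. The rejection probability is Φ(0.96 - 1.96) + Φ(-0.96 - 1.96) = 0.159 + 0.002, about 16%.
- r = 2, s = 0.7: 0.990/0.233 = 4.24. The rejection probability is Φ(4.24 - 1.96), about 99%.

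A small plasma share does little harm. With 12 of 50 controls in plasma, the rate is 5.6%, 7.5% and 14.6% for shifts of 0.25, 0.5 and 1.0 SD.

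**5. Comparison of within-patient changes.** If both of a control's specimens are plasma, the log change is (log y2 - ln r) - (log y1 - ln r) = log y2 - log y1, and a constant shift cancels. If one is serum and the other plasma, a term of size ln(r) remains. The plan neither specifies change scores for this comparison nor requires a control's two specimens to be of one type.

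**6. Cost of restricting to serum.** The difference detectable with 80% power is (1.96 + 0.842) x sqrt(1/29 + 1/m), where m is the number of serum controls. This gives 0.654 SD for m = 50, 0.691 for 38, 0.765 for 25 and 0.935 for 13. The documents do not give the split, so the values of m below 50 are illustrations.

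**The case against.** **The simulated test is not in the plan.** Section 9.1 names paired pre/post tests, then logistic and Cox models, and then says that these effects will be compared with controls. That may mean changes or biomarker-outcome associations rather than levels. A constant shift cancels in log changes under the condition in step 5. In an association model fitted within one group and one specimen type, the intercept absorbs it. This stands: the percentages describe one possible analysis and cannot be read as error rates of the planned one. But section 9.1 does not rule out a comparison of levels, and the condition that would make changes safe is not required.

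**The documents do not show that serum and plasma readings differ.** This also stands. The ratio, the SD and the plasma share are all assumptions, any difference would vary by analyte, and the repository may supply only serum. The plan, however, neither shows equivalence nor restricts the type.

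**Stronger readings that the documents do not support.** A reader might infer that antibody results are affected in the same way. Recipient titers may themselves be serum or plasma, so although the type is uncontrolled, the text does not tie it to group. A reader might also infer from the green-top listing in section 5.2.7 that the recipients' own specimen type varies. That section lists antibody testing on a separate line without naming a tube, and wherever the documents name a specimen for recipient cytokines it is serum. This is an inconsistency between tube lists and does not show that recipients are assayed in plasma.

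**The comparison is secondary and exploratory.** True, and this limits the importance of the point. The primary endpoints and safety are untouched.

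**Conclusion.** The concern holds for cytokines only. Recipients are specified in serum, controls may be either type, and the planned comparison ignores the difference. A serum-plasma difference could therefore be reported as an effect of convalescent plasma if levels are compared, or if changes are compared in controls whose two specimens differ in type.

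The documents do not fix the size. Under the assumptions in step 4, the false-positive rate for a single cytokine would be about 7-50% with half the controls in plasma and 16-99% with all in plasma. It stays at 5% if all controls are serum or the two types read alike. These figures show what is possible under a test of levels; they do not predict the trial's error rate. The consequence is confined to one assay family within a secondary objective, but the remedy is cheap and has to be chosen before control specimens are requested.

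**What to change.** - In sections 1.0 and 2.3 and in the immunologic control criteria, request serum for the cytokine assays where the repository has it. Require both specimens from a control to be of the same type.
- Record specimen type for every recipient and control assay.
- In section 9.1, limit the inferential cytokine comparison to specimens of the same type, and report any mixed comparison as descriptive. State whether levels or within-patient log changes are compared.
- Reconcile the tube list in section 5.2.7 with sections 8.3 and 10.8.

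If serum controls prove scarce, recipient plasma from the green-top tubes could be compared with control plasma. That requires knowing the repository's anticoagulant, which the documents do not give.

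**Cost.** A line in the specimen request, a recorded field and a sentence in the analysis plan, with no extra patients and no blood beyond what sections 8.3 and 10.8 already provide. The real price is possibly fewer cytokine controls: at 80% power the detectable difference rises from 0.654 SD with 50 controls to 0.765 SD with 25, and to 0.935 SD with 13.
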